## 8.3 ADVERSE EVENTS AND SERIOUS ADVERSE EVENTS

### 8.3.1 DEFINITION OF ADVERSE EVENTS (AE)

An adverse event will be defined according to the ICH-GCP as: Any untoward medical occurrence in a patient or clinical investigation subject administered a pharmaceutical product and which does not necessarily have a causal relationship with this treatment. An adverse event (AE) can therefore be any unfavorable and unintended sign (including an abnormal laboratory finding), symptom, or disease temporally associated with the use of a medicinal (investigational) product, whether or not related to the medicinal (investigational) product (see the ICH Guideline for Clinical Safety Data Management: Definitions and Standards for Expedited Reporting).

### 8.3.2 DEFINITION OF SERIOUS ADVERSE EVENTS (SAE)

A serious adverse event will be defined according to the ICH-GCP as: Any untoward medical occurrence that at any dose:

- results in death,
- is life-threatening,
- requires inpatient hospitalization or prolongation of existing hospitalization,
- results in persistent or significant disability/incapacity,

or

- is a congenital anomaly/birth defect (see the ICH Guideline for Clinical Safety Data Management: Definitions and Standards for Expedited Reporting).

---

### 8.3.3 CLASSIFICATION OF AN ADVERSE EVENT

#### 8.3.3.1 SEVERITY OF EVENT

Severity of adverse events will be classified from mild to life-threatening. All classifications are defined as:

- Mild: Awareness of sign or symptom, but easily tolerated
- Moderate: Discomfort enough to cause interference with normal daily activities
- Severe: Inability to perform normal daily activities
- Life Threatening: Immediate risk of death from the reaction as it occurred

#### 8.3.3.2 RELATIONSHIP TO STUDY INTERVENTION

All adverse events (AEs) must have their relationship to study intervention assessed by a member of the investigatory team who examines and evaluates the participant based on temporal relationship and his/her judgment. The degree of certainty about causality will be graded using the categories below. In a clinical trial, the study product must always be suspect. The following scale of relatedness will be used:

- Not related: An adverse event which is not related to the study
- Unlikely: An adverse event for which an alternative explanation is more likely
- Possible: An adverse event which might be due to the study. An alternative explanation is inconclusive. The relationship in time is reasonable; therefore, the causal relationship cannot be excluded.
- Probable: An adverse event which might be due to the study. The relationship in time is suggestive. An alternate explanation is less likely.
- Definite: An adverse event which cannot be reasonably explained by alternative explanation. The relationship in time is very suggestive.

#### 8.3.3.3 EXPECTEDNESS

[name] will be responsible for determining whether an adverse event is expected or unexpected. An adverse event will be considered unexpected if the nature, severity, or frequency of the event is not consistent with the risk information provided in the Investigator's Brochure.

---

### 8.3.4 TIME PERIOD AND FREQUENCY FOR EVENT ASSESSMENT AND FOLLOW-UP

The occurrence of an adverse event or serious adverse event may come to the attention of study personnel during study visits and interviews of a study participant. Participants will be told in the initial study visit that they should report any adverse events they are experiencing after completing any study procedures.

All adverse events including local and systemic reactions not meeting the criteria for serious adverse events will be captured on the adverse event form. Information to be collected includes event description, time of onset, assessment of severity, relationship to study product (assessed by an investigator), and time of resolution/stabilization of the event. All adverse events occurring while in the study must be documented appropriately regardless of relationship. All adverse events will be followed to adequate resolution.

Any medical condition that is present at the time that the participant is screened will be considered as baseline and not reported as an adverse event. However, if the study participant's condition deteriorates at any time during the study, it will be recorded as an adverse event.

---

### 8.3.5 ADVERSE EVENT REPORTING

Each adverse event is to be assessed to determine if it meets the criteria for serious adverse event. If a serious adverse event occurs, expedited reporting will follow local and international regulations, as appropriate.

All adverse events will be reported on the adverse event form. Adverse events should be reported using concise medical terminology on the form for collection of serious adverse event information. [name] will be responsible for completing and signing off all adverse event reports. Adverse drug reactions will be reported to the IRB and Health Canada within 15 days.

---

### 8.3.6 SERIOUS ADVERSE EVENT REPORTING

If a serious adverse event occurs, expedited reporting will follow local and international regulations, as appropriate. Health Canada and IRB requirements for reporting of serious adverse events will be followed.

If a serious adverse event occurs, the PI-Sponsor is to be notified within 24 hours of awareness of the event by any investigator. In particular, if the serious adverse event is fatal or life-threatening, notification to the PI-Sponsor must be made immediately, irrespective of the extent of available adverse event information. In the event that the investigator does not become aware of the occurrence of a serious adverse event immediately, the investigator is to report the event to the IRB and Health Canada within 24 hours after learning of it and document the time of his/her first awareness of the adverse event.

For all serious adverse events, the investigator is obligated to pursue and obtain any relevant information. In addition, an investigator may be requested to obtain specific additional follow-up information in an expedited fashion. In general, this will include a description of the adverse event in sufficient detail to allow for a complete medical assessment of the case and independent determination of possible causality. Information on other possible causes of the event, such as concomitant medications and illnesses must be provided.

Serious Adverse events will be noted and recorded on adverse event recording sheets according to ICH GCP. The standards for reporting serious adverse events, as defined in the ICH guideline (Clinical Safety Data Management: Definitions and Standards for Expedited Reporting, ICH Harmonized Guideline) will be strictly followed by study investigators.

---

### 8.3.7 REPORTING EVENTS TO PARTICIPANTS

Participants in this study will not be informed of any adverse events experienced by other participants. If the investigatory team discovers any incidental findings that suggest the participant seek medical attention, they will be informed immediately, and their participation in the study will be suspended until they have seen a physician. Only once they have obtained written permission from their physician, can they continue participation in the study.

---

### 8.3.8 EVENTS OF SPECIAL INTEREST

There are no events of special interest that are likely to occur other than those discussed in previous sections.

---

### 8.3.9 REPORTING OF PREGNANCY

Upon screening, participants will be required to complete an eligibility questionnaire, which will enquire if the participant is pregnant or planning to be pregnant. If participants indicate they are or are planning to be pregnant they will not be enrolled in the study. All female participants will be required to provide a urine sample in order to complete a urine pregnancy test. If the next study visit occurs more than 30 days after the initial visit, the test will be repeated. If a participant becomes pregnant during study participation they will be withdrawn from the study. Pregnancy will be reported as the reason for withdrawal.

---

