**1 PROTOCOL SUMMARY****1.1 SYNOPSIS**

Title:	The Influence of Cannabis Inhalation During Exercise on Cardiovascular Health and Function: Exploring the Balance of Cannabinoids and Mode of Administration to Decrease Risk and Maximize Benefits
Study Description:	The current study will examine the acute cardiovascular response to cannabis consumption at rest, and when combined with exercise. It will examine the influence of inhalation method, and cannabinoid concentration.
Objectives:	
Primary Objective: Determine the effects of cannabis consumption at rest and during exercise on the human cardiovascular system
 
Secondary Objective: investigate the influence of consumption methods (smoking vs. vaporizing) and cannabinoid balances (i.e. THC vs. CBD). Determine the effects of cannabis consumption on exercise performance

Endpoints:	
Primary Endpoints: Carotid-Femoral Pulse Wave Velocity, Brachial Artery Flow-Mediated Dilation, Cardiac Function (dynamics), Muscle Sympathetic Nerve Activity
 
Secondary Endpoints: Blood Pressure, Heart Rate, Work Completed, Rate Pressure Product, Rating of Perceived Exertion

Study Population:	20, healthy male and female recreational cannabis users aged 19-45yr will be recruited for the current study
Description of Sites/Facilities Enrolling Participants:	All activities will be performed at the Human Performance and Health Research Laboratory in the Department of Human Health and Nutritional Sciences, College of Biological Sciences, at the University of Guelph. All research will be conducted in Guelph, Ontario, Canada. Participants will healthy volunteers.

**Description of Study Intervention:** Participants will consume 100mg of cannabis via smoking or vaporizing. Cannabis consumed will possess THC and CBD ratios of either  $13.6 \pm 2.7\% : <1\%$ , or  $<1\% : 14.5 \pm 2.9\%$ .

**Study Duration:** It is estimated that the current study will require a 12 month period for completion, beginning from the onset of study enrollment, to the completion of data analysis

[figure not shown]
**Participant Duration:** Depending on degree of involvement, participant duration of this study will be either 6 weeks, or 10 weeks.

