### 1.3 SCHEDULE OF ACTIVITIES (SOA)

Procedure	Introductory Visit (Visit 0), Day 0	Exercise Control Visit (Visit 1), Day 7±1 day	Phase I Cannabis Visit (Visit 2), Day 14±1 day	Phase I Cannabis + Exercise Visit (Visit 3), Day 21±1 day	Phase I Cannabis Visit (Visit 4), Day 28±1 day	Phase I Cannabis + Exercise Visit (Visit 5), Day 35±1 day	Phase II Cannabis Visit (Visit 6), Day 42±1 day	Phase II Cannabis + Exercise Visit (Visit 7), Day 49±1 day	Phase II Cannabis Visit (Visit 8), Day 56±1 day	Phase II Cannabis + Exercise Visit (Visit 9), Day 63±1 day
Informed Consent	X									
Eligibility Questionnaire	X									
Physical Activity Readiness Questionnaire	X									
Height	X									
Weight	X	X	X	X	X	X	X	X	X	X
Blood Pressure and Heart Rate	X	X	X	X	X	X	X	X	X	X
Urine Test	X	X	X	X	X	X	X	X	X	X
Inquiry of Changes to Health and Prescription Status		X	X	X	X	X	X	X	X	X
VO 2 Max Test	X									
Pulse Wave Velocity		X	X	X	X	X	X	X	X	X
Brachial Artery FMD		X	X	X	X	X	X	X	X	X
Echocardiography		X	X	X	X	X	X	X	X	X
20 Minute Maximal Cycling Exercise		X		X		X		X		X
Vaporization of High THC Cannabis			X	X				X	X	
Smoking of High THC Cannabis					X	X				
Vaporization of High CBD Cannabis							X			X
Indirect Calorimetry/CPET	X	X		X		X		X		X
Microneurography (MSNA)			X							
Stress Echocardiography			X		X		X		X	
Measurement of Continuous Blood Pressure		X	X	X	X	X	X	X	X	X
ECG	X	X	X	X	X	X	X	X	X	X
Impedance Cardiography		X		X		X		X		X
Drug Effects Questionnaire			X	X	X	X	X	X	X	X

*This study will use a randomized crossover design. Phase I of this study will occur prior to the initiation of phase II. If a participant enters the study in phase II, but did not participate in phase I, they will be required to complete the introductory and exercise control visits. Visits 2-5 and 6-9 will occur in a randomized order, which will be individualized for each participant.*

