## 4 STUDY DESIGN

### 4.1 OVERALL DESIGN

The study will use a randomized cross-over design. It will be structured by division into two phases. Both phases will examine the acute cardiovascular response to cannabis consumption,

both at rest and during exercise. *Phase I* will examine if and how this response differs whether cannabis is smoked or vaporized. *Phase II* will examine how this response is influenced by cannabinoid concentration within inhaled cannabis. Phase II of the current study will use a single-blind design, with participants being unaware of the relative cannabinoid concentrations of the cannabis they consume. Cannabis will be inhaled using methods of smoking (phase I only) or vaporization (phase I and II). Each experimental study visit (study visits 2-9), 100mg of cannabis will be consumed via one of the two aforementioned methods of inhalation, followed by a subsequent rest period, or by 20 minutes of exercise. Primary endpoints will be examined pre- and post-consumption each visit (with the exception of muscle sympathetic nerve activity, which will only be performed on a single study visit), while secondary endpoints will be recorded during exercise.

Each phase of the study will require participants to complete an introductory and control visit, as well as 4 experimental study visits, where cannabis inhaled under alternating conditions (phase I: smoking vs. vaporizing high THC cannabis, phase II: high CBD cannabis vs. high THC cannabis) followed by exercise, or a time-matched rest period. The order in which these visits will occur will be randomized, and individualized for each participant. A within-subjects design will be utilized, so that each participant completes each condition. High THC cannabis used will be the cannabis strain “Rex”, while the high CBD strain will be “Kalea”. The dose size and strength will not be altered throughout the course of the study.

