## 5 STUDY POPULATION

### 5.1 INCLUSION CRITERIA:

To be eligible to participate in each phase study, an individual must meet all of the following criteria:

1. Provision of signed and dated informed consent form
2. Stated willingness to comply with all study procedures and availability for the duration of the study
3. Male or female, aged 19-45yr
4. In good general health as evidenced by medical history and free of chronic disease
5. Must be experienced with cannabis use. This requires recreational cannabis use of a minimum of once per week in the past 30 days as confirmed by urine test
6. Experience consuming cannabis recreationally by vaping dried cannabis

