### 5.2 EXCLUSION CRITERIA

An individual who meets any of the following criteria will be excluded from participation in this study:

1. **Deemed unfit to exercise by the PARQ+.**  
The goal of the present study is to examine the acute cardiovascular response to cannabis consumption at rest and during exercise. As such participants must be able to safely complete the pre-determined exercise protocol.
2. **Current or past diagnoses of substance abuse disorder**
3. **Failure of recreational substance urine screening test**
  - **Substances to be tested for include: Cocaine, Crack, Morphine, Heroin, Fentanyl, Amphetamines, Ecstasy, Methamphetamine, Spice and AB-Pinaca (synthetic cannabis), Methcathinones, LSD, and Ketamine.**
4. **Current, past, or strong family history of psychosis, or has previously experienced a cannabis-related psychotic episode**
5. **Current or past diagnoses of cannabis use disorder**
6. **Current or past diagnoses of any mood or anxiety disorder**  
Exclusion criteria 2-5 will be implemented to ensure that no individuals are enrolled in the study who could carry an elevated risk of experiencing a severe cannabis related adverse event (such as cannabis induced hyperemesis, or a psychotic episode). Each of these exclusion criteria represent contraindications for cannabis prescription.
7. **Identified ECG abnormalities**
8. **Systolic blood pressure exceeding 160mmHg**
9. **Diastolic blood pressure exceeding 90mmHg**
10. **Resting heart rate exceeding 100bpm, or lower than 40bpm**
11. **Diagnosed with respiratory disease**
12. **Diagnosed with cardiovascular disease**
13. **Diagnosed with liver disease**

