## 8 STUDY ASSESSMENTS AND PROCEDURES

### 8.1 EFFICACY ASSESSMENTS

Participants will be screened for eligibility using two separate screening procedures during the introductory visit. The first screening procedure will be an investigator generated eligibility questionnaire. This questionnaire will evaluate whether the participant fits inclusion criteria and does not meet any exclusion criteria. The second screening tool will be the PARQ+, a validated questionnaire designed to determine whether participants are fit to safely exercise. The PARQ+ may determine that a participant requires clearance from their physician. If they do not obtain a signed doctor's note, they will not be eligible to participate. All screening procedures will occur during the introductory visit, and within one week of the exercise control visit. Additionally, at the start of each study visit participants will be asked if there have been any changes to their health status, or prescription medication status.

Efficacy assessments of primary objectives are as follows:

- Arterial stiffness will be assessed before and after cannabis consumption with and without subsequent exercise under each condition, during each study visit. Carotid-femoral pulse wave velocity will be used to determine arterial stiffness. Carotid-femoral pulse wave velocity will be measured by placing a tonometer probe at the site of the carotid and femoral pulse. Pulse waveforms will be juxtaposed against a lead-II electrocardiogram to determine pulse wave velocity.
- Endothelial function will be characterized before and after cannabis consumption with and without exercise under each condition during each study visit. Endothelial function will be measured using brachial artery reactive hyperemic flow-mediated dilation. The brachial artery will be imaged using a General Electric Vivid-i ultrasound system. After 1 minute of imaging, a tourniquet placed on the antecubital fossa will be inflated to 220mmHg for a period of 5 minutes will imaging continues. After this period 3 minutes of ultrasound imaging will be recorded to assess the vasodilatory response to occlusion. The relative (%) change in arterial diameter following release of the tourniquet will be the primary endpoint.

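### The pregnancy re-test rule in Protocol 8.3.9 can be read so that it never applies on schedule, leaving the fourth dosing visit covered only by the Day 0 test

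*Protocol*

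**What the plan says.** Protocol 8.3.9 has all women give urine for a pregnancy test at screening and states one rule for repeating it: "If the next study visit occurs more than 30 days after the initial visit, the test will be repeated." Section 8.1 fixes the timing of screening: "All screening procedures will occur during the introductory visit, and within one week of the exercise control visit." The SoA (1.3) puts Visit 0 on Day 0 and Visit 1 on Day 7±1, then weekly visits to Day 35±1 for Phase I and from Day 42±1 to Day 63±1 for Phase II. Section 4.1 makes all of Visits 2 to 9 dosing visits: "Each experimental study visit (study visits 2-9), 100mg of cannabis will be consumed."

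The protocol is not consistent on what a woman does when she returns for Phase II. Section 4.1 says: "Each phase of the study will require participants to complete an introductory and control visit." Section 5.1 likewise applies eligibility phase by phase: "To be eligible to participate in each phase study, an individual must meet all of the following criteria." The SoA footnote instead asks for the first two visits again only of a Phase II entrant who "did not participate in phase I, they will be required to complete the introductory and exercise control visits." The synopsis says "participant duration of this study will be either 6 weeks, or 10 weeks."

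The SoA has a row labelled Urine Test, marked at all ten visits, which does not say what is tested. It has no separate pregnancy-test row.

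**The concern.** Section 5.2 excludes pregnancy because the fetal effects of cannabis are not established, and sections 7.2 and 8.3.9 make it a reason for withdrawal. Withdrawal depends on detection. The re-test rule compares a single visit, the next one, with a fixed anchor, the initial visit. If the next visit is Visit 1, staff could follow 8.3.9 to the letter and give the Day 35 dose with no pregnancy test since Day 0. Other staff, reading the same sentence as covering any visit past Day 30, would re-test. Both would be compliant.

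The stake is participant safety at a few dosing visits. Required contraception (5.2) and the health inquiry at each visit (7.1) already lower the risk, so the re-test is a backstop. Nothing in the efficacy analysis, sample size or alpha depends on it.

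**Working it through.** **Inputs.** The 30-day trigger is from 8.3.9, visit days and ±1-day windows are from the SoA, and the definition of dosing visits is from 4.1.

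**Step 1: the trigger read literally.** From the initial visit to the next visit is 7±1 = 6 to 8 days, never more than 30. The rule does not apply to any woman on schedule.

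**Step 2: days from Visit 0 to each dosing visit.**

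| Visit | Days since Visit 0 | More than 30? |
|---|---|---|
| 2 | 13–15 | never |
| 3 | 20–22 | never |
| 4 | 27–29 | never |
| 5 | 34–36 | always |
| 6 | 41–43 | always |
| 7 | 48–50 | always |
| 8 | 55–57 | always |
| 9 | 62–64 | always |

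Randomization changes which condition falls on which date, but all four visits of a phase involve cannabis, so the fourth dose is affected in every order. The excess is 34 − 30 = 4 to 36 − 30 = 6 days. Section 5.3 reschedules a visit after a positive THC test, which can only move doses later. A slip of 2 days from Day 29 (29 + 2 = 31), or 4 days from Day 27 (27 + 4 = 31), takes Visit 4 past Day 30 as well.

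**Step 3: by type of participant, literal reading.**
- *Phase I only:* one of four doses, at Day 34–36.
- *Phase II only:* the same, assuming that her dosing visits follow her own introductory visit at the Phase I spacing. The SoA prints only Days 42 to 63 for Phase II visits, so this is an inference.
- *Both phases, SoA footnote governs:* Visit 5 and all four Phase II doses, at Days 34–36 and 41–64. The Phase II excess is 41 − 30 = 11 to 64 − 30 = 34 days.
- *Both phases, section 4.1 governs:* the fourth dose of each phase, assuming the screening test is repeated at the second introductory visit.

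The stated duration fits the footnote better: a second introductory visit on Day 42 would put the last visit on Day 42 + 35 = 77, which is 11 weeks against the 10 stated. That does not resolve the conflict.

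**Step 4: the other reading.** If the rule covers any visit more than 30 days after the initial visit, a re-test is due at Visit 5 and, for a woman in both phases without a second introductory visit, at Visits 6 to 9 as well. No dosing visit is then uncovered.

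**Step 5: the urine row.** The THC check in 5.3 is set out for experimental visits, which 4.1 defines as Visits 2 to 9. At Visit 0 the row must also hold the drug screen behind the exclusion "Failure of recreational substance urine screening test" and the pregnancy test of 8.3.9. It is therefore not a THC-only row, and it could carry pregnancy testing forward. Against that, testing at every visit would make the 30-day sentence redundant. The row settles nothing either way.

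**The case against.** The strongest reply is that the literal reading is the weaker one. Section 8.1 already ties screening to within a week of Visit 1, so a rule about Visit 1 falling more than 30 days later has no work to do in a compliant participant. Reading the sentence as covering any upcoming visit past Day 30 gives it a purpose and may well be what was meant. The urine row may also already include pregnancy. This stands: the evidence shows an unclear rule, not untested women.

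A second reply is that the literal rule sets no rolling standard. It can be taken as a limit on how old the screening test may be at the start, and applying 30 days to each dose is a yardstick brought to the text. This also stands, although the figure itself is the protocol's.

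A reader might go further and put a percentage on the gap. Section 5.5 plans 10 women per phase, so there are 10 × 4 × 2 = 80 female dosing visits. The literal reading gives 20 of 80 (25%) if no woman does both phases, rising to 50 of 80 (62.5%) if all 10 do and the footnote governs. The documents do not support these as the size of the problem. They require the literal reading, the higher figure also requires an overlap that is nowhere stated, and half of the 20 rests on the inferred Phase II-only dates. On the second reading, or if the urine row covers pregnancy, the count is 0 of 80.

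**Conclusion.** The point holds as a minor ambiguity of wording with a safety consequence. On the literal reading, the fourth dosing visit after screening takes place 4 to 6 days beyond the protocol's own 30-day figure with no explicitly required re-test, and later if visits slip. Under the SoA footnote the same is true of every Phase II dose for a woman in both phases. On the alternative reading, or with pregnancy included in the urine row, there is no gap.

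A reader might infer that women will be dosed without a current test. The documents do not establish that; they leave it open. The conclusion assumes the planned schedule with its ±1-day windows and takes 8.3.9 as the only text that explicitly calls for a pregnancy test. Confidence is medium because the intended meaning may be the benign one, which is a reason to state it.

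**What to change.** Reword the sentence in 8.3.9 to: *The urine pregnancy test will be repeated, before cannabis dosing, at any study visit occurring more than 30 days after the participant's last pregnancy test, including on return for Phase II.* Add a pregnancy-test row to the SoA, separate from the THC and drug-screen tests. This works whether section 4.1 or the SoA footnote governs re-entry, although that conflict should be settled in its own right.

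The cost is one sentence, one row and a few strips on urine already collected. On schedule, a woman in one phase needs 1 extra strip, at Visit 5. A woman in both phases needs 2 if section 4.1 governs. Under the footnote she needs 1, because Visit 9 comes 28 days after Visit 5 (26 to 30 with windows), not more than 30. Under the footnote a late Phase II can make it 2: possible from a 1-day delay (30 + 1 = 31) and certain from 5 days (26 + 5 = 31). It is never more than 2, since Visits 6 to 9 span at most 21 + 2 = 23 days. In total that is 20 × 1 = 20 strips with no overlap, or 10 × 1 = 10 to 10 × 2 = 20 with full overlap. Keeping the anchor at the initial visit under the second reading would use 20 × 1 = 20 to 10 × 5 = 50, so re-anchoring to the last test costs no more.
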